11. SECONDARY SAFETY ANALYSES

11.1. ASSESSMENT OF THE DEVICE CHARACTERISTICS IN TERMS OF SAFETY AND DEVICE DEFICIENCY

- A. Serious adverse device events and device deficiencies will be collected during each subject visit. Confirmation of absence of USADE during “In-Clinic LVAT” tests will be evaluated by analyzing all SAEs and device deficiencies (DD) collected at each visit.

This secondary endpoint will be based on IP.

- B. Algorithm characteristic: Underestimated Assessments

Assessment of LV pacing threshold underestimation: comparison to manual LV threshold value will be performed by comparing manual and automatic LV threshold values at each visit. An underestimated LV threshold value of “In-Clinic LVAT” feature is defined as a value result more than 2 steps below the LV threshold measured manually (meaning -0.5V if threshold<2.5V, else -1V as measured) . Please see table 6.

LEVEA – Statistical Analysis Plan

Number and percentages of “underestimated” assessments will be presented along with the exact 95% CI (Clopper & Pearson, 1934) by M0 and M1 visit. Only subjects with non-missing manual data will be considered.

The reasons for LV pacing threshold underestimation at M0 visit will be presented as table and listing. The missing reasons (if any) for underestimation will be presented as “Not available”. For the table, the number and percentages of the reasons will be presented with the denominator of the percentages based on the total number of LV pacing threshold underestimated.

Total number of attempted, completed,, Underestimated LV vector tests will be presented by LV vector for each LV pacing configuration by visit.

For the LV tests performed for patients with either IS1 and IS4 leads (six LV vectors common to IS1 and IS4) , the percentage for the number of LV vector tests “attempted”, will be calculated based on the number of patients implanted with either IS1 and IS4 leads.

For the LV tests performed for patients with IS4 leads (eight LV vectors pertaining only to IS4), the percentage for the number of LV vector tests “attempted”, will be calculated based on the number of patients implanted with IS4 lead.

For number of LV vector tests “completed”, the percentage will be calculated based on the number of LV vector tests attempted.

For number of LV vector tests “Underestimated”, the percentage calculated based on number of Complete LV vector tests .

A heat plot will be presented for Attempted, Complete, Underestimated percentages. If the percentage is > 90%, it will be coloured green, if the percentage is between 75% and 90% (inclusive), it will be coloured brown and if the percentage <75%, then it will be coloured orange.

This Secondary endpoint will be based on EP population and will also be listed.

C. Analysis of Unexpected Function Operations

Number and percentage of unexpected function operations by analyzing EGM collected in the RTD files and ECG (from DDD A-test) performed during “In-Clinic LVAT” test at each visit will be presented.

- i. Number and percentage of LV vector tests with unexpected functions based on all LV vector tests attempted.
- ii. Number and percentage of LV vector tests with unexpected functions per LV vector per LV pacing configuration per visit

Total number of attempted, completed, with expected function, with unexpected function LV vector tests will be presented by LV vector for each LV pacing configuration by visit.

For the LV tests performed for subjects with either IS1 and IS4 leads six LV vectors common to IS1 and IS4), the percentage for the number of LV vector tests

LEVEA – Statistical Analysis Plan

“attempted”, will be calculated based on the number of subjects implanted with either IS1 and IS4 leads.

For the LV tests performed for patients with IS4 leads (eight LV vectors pertaining only to IS4), the percentage for the number of LV vector tests “attempted”, will be calculated based on the number of patients implanted with IS4 lead.

For number of LV vector tests “completed”, “with Unexpected Function” and “with Expected Function”, the percentage will be calculated based on the number of LV vector tests attempted .

The reasons for unexpected assessment at M0 visit, M1 visit and overall will be presented as table and listing. The missing reasons (if any) for unexpected assessment will be presented as “Not available”. For the table, the number and percentages of the reasons will be presented with the denominator of the percentages based on the total number of unexpected assessments.

All unexpected function operations will be listed.

This Secondary endpoint will be based on EP population.

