8.2. ANALYSIS POPULATION

The analysis populations will be reviewed and determined during the Data Review meeting based on all included subjects. The included population will consist of all subjects who have completed "Inclusion Form".

The main analysis populations are:

- The Intention To Treat (ITT) population will consist of all included subjects with at least 1 eligible complete LV Vector Tests at M0 follow-up (if unavailable, M1 follow-up will be considered). This population will be used for the assessment of the primary endpoint (see section 4.1.2).
- The M0-Intention To Treat (M0-ITT) population will consist of all included subjects with at least 1 eligible complete LV Vector Tests at M0 follow-up. This population will be used for the assessment of the secondary endpoints concerning the LV test done at M0 follow-up (see section 4.1.3).
- The M1-Intention To Treat (M1-ITT) population will consist of all included subjects with at least 1 eligible complete LV Vector Tests at M1 follow-up. This population will be used for the assessment of the secondary endpoints concerning the LV test done at M1 follow-up (see section 4.1.3).
- The included population will be used for the assessment of the secondary endpoint “Applicability of the algorithm” (see section 4.1.3).
- The safety population will consist of all subjects included and implanted with Platinium SonR CRT-D 1811, 1841 or 1844. The number of subjects in each population will be mentioned in the disposition of subjects.
- Ancillary population will consist of all included subjects with at least one right ventricular pacing electrogram collected during RV A-test or RV P-test at M0 or/and M1 follow-up (see section 4.1.4).

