8.6. SAFETY ANALYSIS

The secondary objective of assessing safety and device deficiencies of the compound will be answered by summarizing the relevant endpoints by means of descriptive statistics on the Safety population.

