6. ANALYSIS POPULATION

6.1. INCLUDED POPULATION (IP)

The included population consists of all subjects included in the study who have completed “Inclusion Form”.

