6.2. EVALUABLE POPULATION (EP)

The evaluable population will consist of IP excluding the subjects having a protocol deviation on “Eligibility Criteria: Right atrial, right and left ventricles lead must be implanted. Only Bipolar or quadripolar for left ventricular lead”. A subject whose termination date occurred prior to M0 visit, will be excluded from this population.

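### SAP 11.1 B and C use a set that can drop LVAT-tested subjects, contrary to CIP 8.6 and undeclared, and no defined set gives test-period safety events a denominator of exposed subjects

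*SAP*

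**What the plan says.** The item under investigation is the In-Clinic LVAT software function. The CRT-D that carries it is CE-marked and is listed as not under investigation (CIP 5.1.1 and 5.1.2). The function is first launched at M0, up to 15 days after inclusion (CIP 6.1.2; SAP 5.3).

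The protocol answers the safety and deficiency objective by "summarizing the relevant endpoints by means of descriptive statistics on the Safety population" (CIP 8.6). CIP 8.2 defines that set: "The safety population will consist of all subjects included and implanted with Platinium SonR CRT-D 1811, 1841 or 1844".

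SAP 11.1 divides the objective:

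- Part A: the absence of USADEs during LVAT tests "will be evaluated by analyzing all SAEs and device deficiencies (DD) collected at each visit", with the instruction "This secondary endpoint will be based on IP". On IP, SAP 6.1 says: "The included population consists of all subjects included in the study who have completed" the Inclusion Form.
- Part B, underestimation, and part C, unexpected function operations: "This Secondary endpoint will be based on EP population". On EP, SAP 6.2 says: "The evaluable population will consist of IP excluding the subjects having a protocol deviation on" the lead criterion (all three leads implanted, LV lead bipolar or quadripolar). It adds: "A subject whose termination date occurred prior to M0 visit, will be excluded from this population".

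SAP 14.1 and 14.2 present adverse events for a Safety population. SAP section 6 defines IP, EP, ITT, M0-ITT, M1-ITT, AP and PP, but no Safety population, and the disposition list in SAP 7.1 omits it too. SAP 3.1 marks changes from the protocol as not applicable, whereas CIP section 8 asks for relevant major changes to the analysis to be made by amendment or set out in the SAP with a rationale.

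**The concern.** For a function that acts only while a test is running, the subjects who inform its safety are those in whom a test was launched. None of the SAP's sets is defined that way, and the sets used depart from it in opposite directions.

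For B and C, the exclusion for a lead deviation does not ask whether the subject was tested. If such a subject was tested and the algorithm underestimated the threshold or behaved unexpectedly, that result drops out of the endpoint meant to capture it. CIP 7.1 names underestimation of the threshold, through anodic stimulation or fusion, among the main risks. An eligibility breach is a usual reason to leave a subject out of a performance analysis, but a poor one to leave an exposed subject out of a safety analysis.

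For A and SAP 14, subjects who leave between inclusion and M0 stay in the set. SAP 7.1 tabulates that path, so the plan foresees it. They cannot have an event during an LVAT test. If a per-subject rate or limit is computed for test-period events, they enlarge the denominator without having been at risk.

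**Working it through.** **1. The sets against exposure to the function**

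| Set | Entry rule | Can hold never-tested subjects? | Can omit tested subjects? |
|---|---|---|---|
| IP (SAP 6.1) | Inclusion Form completed | Yes | No |
| Safety (CIP 8.2) | Included and implanted | Yes | No |
| EP (SAP 6.2) | IP, less lead deviations, less terminations before M0 | Yes, if no test was launched although the subject stayed | Yes, if a lead deviation |
| ITT (SAP 6.3) | EP with at least one eligible complete test | No | Yes: lead deviation, or only aborted or interrupted tests |

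Inclusion requires an implanted study device (CIP 4.4), so IP and the protocol's Safety population are nearly the same. Part A therefore follows the protocol in substance; B and C do not.

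**2. The plan's own figures** (SAP 2.3: target 90%, expected 95%, one-sided alpha 2.5%, power 80%, attrition 20%)

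- Exact binomial with n = 231: reject at 217 or more successes; alpha 0.0239, power 0.816. The 231 reproduces.
- 231/5 = 46.2, so 47 subjects; 47/(1 − 0.20) = 58.75, so 59 enrolled.
- 59 − 47 = 12 subjects, or 12/59 = 20.3%.

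Neither document states a safety rate or safety precision.

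**3. Effect of the denominator on test-period events**

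With 0 events the upper end of the exact two-sided 95% interval is 1 − 0.025^(1/n). With x > 0 it is the Clopper-Pearson limit, the 0.975 quantile of Beta(x + 1, n − x). The number lost before M0 is not given, so it is varied from 0 to 12 as an assumption.

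| Lost before M0 | Tested | Upper limit, 0 events |
|---|---|---|
| 0 | 59 | 6.06% |
| 3 | 56 | 6.38% |
| 6 | 53 | 6.72% |
| 9 | 50 | 7.11% |
| 12 | 47 | 7.55% |

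With events, 59 against the worst case of 47:

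- 1 event: 1.69% (upper limit 9.09%) against 2.13% (11.29%).
- 2 events: 3.39% (11.71%) against 4.26% (14.54%).

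The ratio of rates is 47/59 = 0.80, so a per-subject rate on IP is at most about 20% too low in relative terms under the planned attrition.

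**4. Subjects lost from B and C**

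No count of tested subjects with a lead deviation is given. If it were 1 to 4 out of 47 tested (an assumed range), 1/47 = 2.1% to 4/47 = 8.5% of tested subjects would leave B and C, together with any underestimation or unexpected operation they had.

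**The case against.** The strongest reply is that little of this reaches a reported number.

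- A reader might infer that untested subjects are counted as event-free. The SAP does not say so. Part A gives no rate or denominator, and whether a USADE occurred does not depend on one. IP is the widest set and cannot lose an event. SAP 17.2 gives two rules, the size of the analysis population and, by default for categorical data, the number with non-missing information, so the dilution is not forced. This stands. Still, CIP 8.5.2 plans point estimates and 95% intervals wherever possible, and SAP 14.2 counts subjects with at least one event, so a per-subject rate is a likely product.
- With fewer than 10 adverse events in the study, SAP 14.1 presents them by listing only. The 0, 1 and 2 event cases above may then never be tabulated. This stands too.
- Part A also covers events reportable from consent to termination, for which all included subjects is the right set. This stands, and the fix keeps it.
- A reader might infer that B and C are diluted as well. They are not in their main results: underestimation is a percentage of complete vector tests and unexpected operation a percentage of attempted vector tests, so untested subjects add nothing.
- EP removes tested subjects only if someone with a lead deviation was tested. Subjects without an LV lead could not be, and those who left before M0 were not. So EP can drop tested subjects; the documents do not show that it does. Other breaches could leave testing partly possible, and the exclusion rule does not distinguish them.
- Listings give some protection: SAP 11.1 C lists unexpected operations and SAP 17.1 promises listings of all data. That helps a careful reader but does not put the result into the endpoint.
- Not evaluable is not the same as not tested. A subject whose tests were aborted or lacked a manual pair was exposed, and the window before M0 is at most 15 days. Losing all 12 before M0 is an extreme bound.

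**Conclusion.** The point holds in a limited form. As written, the SAP can remove tested subjects' underestimations and unexpected operations from 11.1 B and C, which departs from the population named in CIP 8.6 without being declared. SAP 14 rests on a population the SAP does not define. These follow from the text alone; how many subjects are affected is unknown.

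The denominator effect in 11.1 A and SAP 14 is conditional and small. If a per-subject rate or limit is given for test-period events, the zero-event upper limit shifts from 6.1% to 6.7% with 53 tested, and to 7.5% at the extreme, always in the favourable direction. This assumes 59 included and an invented split of the planned attrition. No safety hypothesis or threshold depends on it.

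The documents do not support the stronger reading that the safety rates of the function are understated: no per-subject rate is specified in part A and no event is lost there. Nor is this necessarily the only safety evidence on the function, since CIP 7.1 and 7.3 refer to a risk analysis, bench testing and software validation. The change is worth making before analysis because it corrects an undeclared departure from the protocol and costs almost nothing.

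**What to change.** 1. Define the Safety population in SAP section 6 and add it to the disposition in SAP 7.1.
2. Add a tested set: subjects with at least one In-Clinic LVAT test launched, by visit and overall, whatever their eligibility deviations. Base it on launch. The wording for an attempted test in SAP 5.7 and its Table 3 disagree on whether aborted or interrupted tests count.
3. Use the tested set as the denominator for AEs, SADEs and USADEs during testing, and as the population for 11.1 B and C. Keep the per-test denominators in B and C.
4. Keep IP or the Safety population for events counted from consent to termination.
5. Declare the change, with its reason, in SAP 3.1.

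The cost is some SAP wording, one extra flag and slightly less favourable upper limits. The sample size and the primary analysis are unaffected.

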4.1.2. Primary endpoint

The primary endpoint of the study is the success rate of “In-Clinic LVAT” test.

The success is defined by a LV threshold value identified automatically by “In-Clinic LVAT” feature equivalent to the manual threshold test value performed by physician on at least 90% among complete tests (performance goal).

For the primary endpoint, the evaluation is performed on 5 LV pacing vectors common to IS1 and IS4 leads: LV bipolar, LVring-RVcoil, LVtip-can, LVtip-RVcoil, and LVring-can pacing vectors. Test will be evaluated at different pacing conditions: DDD A-test and VVI. Results will be analyzed irrespective of the type of lead used (bipolar or quadripolar) and in any test configuration (DDD A-test or VVI).

An equivalent LV threshold value is defined as the same value of automatic and manual LV threshold tests, with a flexibility of ± 2 steps (meaning $\pm 0.5V$ if threshold $< 2.5V$, else $\pm 1V$ as measured in 2 consecutive cardiac cycles). A margin of ± 2 steps is accepted because of the variability of the threshold, and due to the design of the algorithm.

Among all the eligible complete LV Vector Tests collected, only those performed in DDD A-test with atrial overdrive pacing configuration (if available, otherwise in VVI) and with a manual LV threshold test performed in the same conditions and reported in the electronic Case Report Form (eCRF) will be retained. Only one LV Vector Test per LV pacing vector per subject will be analyzed.

In case several LV Vector Tests were eligible with the same LV pacing vector, for the same subject, on 2 different follow-ups, only M0 data will be considered.

The primary analysis is based on at least 231 complete LV Vector Tests provided by the algorithm and collected at M0. If data at M0 is unavailable, then corresponding data collected at M1 will be considered.

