6.1. TREATMENT AND EVALUATION

6.1.1. *Inclusion follow-up*

Subjects must be informed about the investigation and the potential benefits and risks of the study prior to enrollment. Only those subjects who voluntarily provide written consent to participate will be eligible for enrollment.

The following procedures must be conducted before inclusion of the subject in the study:

- Evaluate subject eligibility based on the inclusion and exclusion criteria
- Obtain written informed consent
- Source data that demonstrate conformance with inclusion criteria should be retained at the investigational site

The following procedures must be conducted in order to include the subject in the study:

- Report implant information
- Report subject's medical history
- Report subject's clinical examination including current vital signs and NYHA classification
- Report subject's current concomitant medications (based on the EDC questions)

6.1.2. *M0 follow-up*

- Perform a complete interrogation of the device with the appropriate clinical programmer
- Print report file
- Measure P-R, A-R and V-V inter ventricular conduction durations on the EGM
- Launch manual LV threshold tests on:
 - 5 common LV vectors to IS1 and IS4 for all subjects,
 - 4 dedicated IS4 LV vectors for subject implanted with IS4 LV lead (LV2-LV4, LV3-LV4, LV3-LV2, LVtip1-LV4).

Manual tests should be performed prior to automatic test to limit bias.

Optional manual threshold tests on additional LV pacing vectors could be performed under physician discretion.

- ECG record:
 - Spontaneous rhythm,
 - Paced rhythm during “In-Clinic LVAT” test in DDD A-test for 30 seconds recording corresponding to 10 seconds before launching test and 20 seconds during the test.
- Launch “In-Clinic LVAT” test on all LV pacing vectors in following pacing configuration:
 - DDD A-test
 - DDD P-test
 - VVI
- Perform right ventricular pacing recordings data collection using RF telemetry to allow collection of multiple EGM:
 - RV A-test

- RV P-test
- Retrieve subject technical data analysis files
- Report Adverse Events and Serious Adverse Events occurred during the testing procedure if any
- Report Device Deficiencies if any

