6.1.3. M1 follow-up

- Perform a complete interrogation of the device with the appropriate clinical programmer
- Print report file
- Measure P-R, A-R and V-V inter ventricular conduction durations on the EGM
- Launch manual LV threshold tests on:
 - 5 common LV vectors to IS1 and IS4 for all subjects,
 - 4 dedicated IS4 LV pacing vectors for subject implanted with IS4 LV lead (LV3-can, LV3-RVring, LV3-RVcoil, LV4-RVcoil).

Manual tests should be performed prior to automatic test to limit bias.

Optional manual threshold tests on additional LV pacing vectors could be performed under physician discretion.

- ECG record:
 - Spontaneous rhythm,
 - Paced rhythm during “In-Clinic LVAT” in DDD A-test for 30 seconds recording corresponding to 10 seconds before launching test and 20 seconds during the test.
- Launch “In-Clinic LVAT” test on all LV pacing vectors in following pacing configuration:
 - DDD A-test
 - DDD P-test
 - VVI
- Perform right ventricular pacing recordings data collection using RF telemetry to allow collection of multiple EGM:
 - RV A-test
 - RV P-test
- Retrieve subject technical data analysis files
- Report Adverse Events and Serious Adverse Events occurred during the testing procedure if any
- Report Device Deficiencies if any
- Report Serious Cardiovascular Adverse Event occurred since last follow-up if any

6.1.4. *Unscheduled follow-ups*

If the subject comes in due to a serious cardiovascular adverse event, re-intervention, or if the subject’s device is interrogated for any reason outside of regular follow-up, the routine follow-up procedure should be performed when possible.

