2.3. SAMPLE SIZE CALCULATION

The study primary objective will be met in case the null hypothesis that the success rate of the “In-Clinic LVAT” is lower than 90% is rejected.

The following assumptions were made to calculate the sample size:

- Power = 80%
- One-sided alpha = 2.5%
- Null Hypothesis proportion of success-rate (target) = 90%

LEVEA – Statistical Analysis Plan

- Expected success-rate = 95%

With these assumptions, it is required to carry out at least 231 LV vector tests. As we will have 5 different pacing vectors for each subject, we will need 47 ($\sim 231/5$) subjects.

An attrition rate of 20% is expected for this study.

Thus the number of subjects needed to be enrolled to obtain 47 evaluable subjects = $47/(1-0.2) = 59$ subjects.

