For number of LV vector tests “completed”, the percentage will be calculated based on the number of LV vector tests attempted and for number of LV vector tests “accurate”, the percentage calculated based on number of Complete LV vector tests .

A heat plot will be presented for Attempted, Completed and Accurate percentages. If the percentage is > 90%, it will be coloured green, if the percentage is between 75% and 90% (inclusive), it will be coloured brown and if the percentage <75%, then it will be coloured orange.

This will also be listed.

For this analysis, EP will be used considering M0 visit only.

10.2. ASSESSMENT OF THE SUCCESS RATE OF “IN-CLINIC LVAT” TEST AT M0 VISIT: COMPARISON TO MANUAL LV THRESHOLD TESTS RESULTS

This endpoint is the success rate of “In-Clinic LVAT” feature on LV pacing vectors and LV pacing configurations available at M0 visit.

The threshold obtained from the “In-Clinic LVAT” feature, extracted from RTD files, will be compared against manual LV threshold values recorded in the eCRF. The definition of equivalence is same as that of primary analysis.

Test will be evaluated at different LV pacing configuration: DDD A-test, DDD P-test and VVI test. Among all the eligible complete LV Vector Tests collected, only those with a manual LV threshold test performed in the same conditions (same pacing pulse width) at M0 visit and reported in the electronic Case Report Form (eCRF) will be retained.

All analyses performed for this Secondary endpoint will be performed based on manual LV threshold tests results considering data only from M0 visit (except for testing of hypothesis and missing data imputation).

This Secondary endpoint will be based on M0-ITT population.

Decomposition of “In-Clinic LVAT” Success Rate by LV Vector and by LV pacing configuration at M0 visit

Only subjects with non-missing manual data will be considered.

Total number of attempted, completed and successful LV vector tests will be presented by LV vector for each LV pacing configuration.

For number of LV vector tests “attempted”, the percentage will be calculated based on the EP population.

For number of LV tests “completed”, the percentage will be calculated based on the number of LV vector tests attempted.

For number of LV vector tests “Successful”, the percentage will be calculated based on number of Complete LV vector tests.

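### SAP 11.1 B divides underestimated tests by all complete tests, so vectors with no scheduled manual reference would show 0% in the by-vector table

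*SAP*

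**What the plan says.** **Definition.** SAP 5.7 (Table 6) and 11.1 B call an automatic threshold underestimated when it lies more than two steps below the manual threshold. SAP 5.7 calls a test complete when it was neither aborted nor interrupted and the algorithm gave a value. No manual value enters that definition.

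**Schedule.** At both visits the automatic test runs on all vectors in three configurations (CIP 6.1.2 and 6.1.3). That is up to 6 vectors for an IS1 lead (SAP 10.4) and 14 for an IS4 lead (SAP Table 2). The required manual tests are narrower. They cover five vectors common to both leads, and the only list of five in the CIP is in 4.1.2: "LV bipolar, LVring-RVcoil, LVtip-can, LVtip-RVcoil, and LVring-can pacing vectors". For IS4 leads, M0 adds "4 dedicated IS4 LV vectors for subject implanted with IS4 LV lead (LV2-LV4, LV3-LV4, LV3-LV2, LVtip1-LV4" and M1 adds a different set, "LV3-can, LV3-RVring, LV3-RVcoil, LV4-RVcoil". Manual tests on further vectors are optional at either visit.

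**Analysis.** SAP 11.1 B first gives an overall underestimated percentage with an exact confidence interval by visit, without naming its denominator. Directly after that comes the section's only manual-data filter: "Only subjects with non-missing manual data will be considered". A table and heat plot by vector, configuration and visit follow, for all six common and eight IS4-only vectors. Attempted tests are a share of the patients with the lead, completed tests a share of those attempted, and then: "For number of LV vector tests “Underestimated”, the percentage calculated based on number of Complete LV vector tests". On causes, the section says: "The reasons for LV pacing threshold underestimation at M0 visit will be presented as table and listing".

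**Elsewhere.** CIP 4.1.3 e keeps, for this endpoint, only tests with a manual test done under the same conditions and reported in the eCRF. SAP 9.1.2 writes the test-level exclusion out for the primary endpoint. The version 1.1 entry in SAP 3.2 describes such a rule for every endpoint comparing algorithm and manual values.

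**The concern.** A complete test without a manual value can enter the denominator but can never be counted as underestimated. The filter in 11.1 B works by subject, and a subject with a manual value on any vector passes it. Every subject is scheduled for five manual tests per visit, so the filter removes almost nobody and leaves the unreferenced tests in.

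The by-vector table would then report zero underestimation on vectors where it was not assessed. CIP 7.1 names underestimation among the main risks, and CIP 4.1.3 e makes it a focus of the device-deficiency endpoint. The heat plot would not help a reader, because every percentage below 75% gets the same colour, so an unmeasured 0% looks like a measured one.

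The reasons table adds a smaller gap. Four IS4-only vectors have scheduled manual tests at M1 only, so an M0-only table of reasons has no scheduled data on them.

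**Working it through.** **Plan figures.** The documents give no expected underestimation rate, so this endpoint has no planned figure to reproduce. The number of subjects used below is the 47 evaluable in SAP 2.3, and it checks. An exact one-sided binomial test of 90% against 95% at 2.5% with n = 231 rejects at 217 or more successes (attained level 0.0239, power 81.6%). 231/5 = 46.2, so 47 subjects; 47/0.8 = 58.75, so 59 enrolled.

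**Step 1: vectors without a scheduled manual test.** SAP Table 2 set against CIP 4.1.2, 6.1.2 and 6.1.3:

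| Visit | Automatic vectors | Scheduled manual | No scheduled manual test |
|---|---|---|---|
| M0 | 14 | 5 + 4 = 9 | LVtip-RVring, LV3-RVring, LV3-RVcoil, LV3-CAN, LV4-RVcoil |
| M1 | 14 | 5 + 4 = 9 | LVtip-RVring, LVtip1-LV4, LV2-LV4, LV3-LV2, LV3-LV4 |

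LVtip-RVring is the only vector missing at both visits. Each of the eight IS4-only vectors is scheduled at exactly one.

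**Step 2: by-vector table.** For a vector with r referenced tests among c complete tests, of which u are underestimated, the literal rule gives u/c and the test-level rule gives u/r. With no optional manual tests:

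- Unreferenced row: r = 0, so u = 0. The literal rule prints 0%; the test-level rule leaves the cell not evaluable.
- Row with scheduled manual tests, all done: r = c, so the two rules agree.

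The effect is therefore confined to 5 of 14 rows per visit. Over three configurations and two visits that is 5 × 3 × 2 = 30 of 14 × 3 × 2 = 84 cells.

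**Step 3: overall rate, only if its denominator were also all complete tests.** Per visit and configuration, with all automatic tests complete and no optional manual tests, an IS1 subject has 5 referenced tests of 6 (0.833) and an IS4 subject 9 of 14 (0.643). With k1 IS1 and k4 IS4 subjects, factor = (5·k1 + 9·k4)/(6·k1 + 14·k4). The documents do not give the IS4 share, so the whole range is shown for 47 subjects, with an assumed true rate of 5% as illustration:

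| k1 / k4 | Referenced / complete | Factor | 5% would read |
|---|---|---|---|
| 47 / 0 | 235 / 282 | 0.83 | 4.2% |
| 35 / 12 | 283 / 378 | 0.75 | 3.7% |
| 23 / 24 | 331 / 474 | 0.70 | 3.5% |
| 12 / 35 | 375 / 562 | 0.67 | 3.3% |
| 0 / 47 | 423 / 658 | 0.64 | 3.2% |

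For example, with 23 IS1 and 24 IS4 subjects and 17 underestimated tests, 17/331 = 5.1% (exact 95% CI 3.0 to 8.1) would become 17/474 = 3.6% (2.1 to 5.7). Optional manual tests move every factor towards 1.

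**The case against.** The best defence is that the plan already holds the right rule. CIP 4.1.3 e restricts this endpoint to tests with a matching manual test, and SAP 3.1 declares no change from the CIP. The note under SAP Table 6 sets an absent manual value to missing, and the version 1.1 history entry words the restriction by test. On that view the subject-level sentence is loose drafting and no 0% cell need appear. The derivation specification named in SAP section 18 may settle the programming, but it is not among the documents.

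This shows intent but does not remove the problem. The denominator sentence and its filter are the operative instruction for the table. The Table 6 note labels the value and does not take the test out of the complete count. The history entry is evidence of intent only; the discrepancy that matters is with the CIP and with the explicit wording of SAP 9.1.2.

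Four stronger inferences are tempting, and the documents do not support them:

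- That LVtip-RVring never gets a manual value, or that an IS4-only vector can get one at a single visit only. Optional manual tests are allowed at both visits.
- That the overall underestimation rate is diluted. The quoted denominator governs the by-vector table. The overall rate has no stated denominator and sits next to the filter, so Step 3 is conditional.
- That unreferenced vectors would read 0% successful in SAP 10.2 and 10.3. Section 10.2 itself keeps only tests with a matching manual test, and 10.3 follows it. Only the repeated subject-level sentence in the decomposition is out of line.
- That underestimations at M1 go unreported. They are counted and listed; only their reasons are not tabulated.

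**Conclusion.** The by-vector denominator in SAP 11.1 B is wrong as written. Followed literally, and without optional manual tests, 5 of 14 vector rows per visit would show 0% underestimated with nothing measured against a reference, contrary to CIP 4.1.3 e. Rows with complete manual data are unaffected.

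For the overall rate, the finding is that the denominator is unstated. The factor of about 0.64 to 0.83 applies only if all complete tests were used, all automatic tests complete, and no optional manual tests are done. The 5% rate is illustrative.

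The row count takes the five common vectors to be those listed in CIP 4.1.2, which SAP Table 7 repeats. The endpoint is secondary and descriptive, and neither the primary test nor the sample size changes. This should be corrected, but it does not threaten the main conclusion.

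**What to change.** 1. In SAP 11.1 B, for both the overall rate and the by-vector table and heat plot, define the denominator of underestimated tests as complete LV vector tests with a non-missing manual value for the same vector, pulse width and visit. Where it is zero, print *no manual reference* instead of a percentage or colour.
2. In the 10.2 and 10.3 decompositions, reword the subject-level sentence to match the test-level rule that 10.2 already states.
3. Tabulate reasons for underestimation at M1 and overall as well as at M0, as 11.1 C does for unexpected operations.

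The cost is SAP wording, a small change to the tables, and assigning reasons to M1 underestimations from recordings the CIP already collects. Denominators will be smaller and the reported rate possibly less favourable. No new subject data are needed.
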